4.3 Schedule of assessment for each visit

Blood sampling- a 5mL blood sample will be obtained from the participant. Serum will be obtained by centrifugation at 3,000 rpm for 10 min and stored at 4°C until analysed. Alternatively the serum may be stored at -80 degrees C until analysis.

Faecal samples will be collected by participants onto the spatula within in a 5mL faecal collection universal container. Samples will be stored at 4°C and will be analysed within 3 days to prevent degradation. Samples will be serially diluted prior to analysis to optimize wavelength detection.

Samples will be subject to Raman analysis with the aim of optimising excitation wavelength and spectral reproducibility. The Raman system (InVia Renishaw) is capable of both 785 nm and 532 nm studies. Comparisons across different patient groups will help determine the best wavelength conditions for reliable data acquisition, sample handling and data reproducibility. Unlike previous published studies, laser power degradation effects on the sample will be tested, as reproducibility is key in identifying the origins of spectral differences from the patient groups. To overcome the inefficiency of Raman scattering it is proposed that through using multiplexed surface-enhanced Raman scattering (SERS) gold nanoparticles functionalised to specific surface markers a unique spectral pattern will be identified. We will analyse blood, faeces and the reference biopsy sample with combinations of functionalised Ag-nanoparticles (labelled with EpCAM, CD44, MUC-1, CK20, CEA) and analyse the resultant spectral peaks and be compared to positive controls. These tests will give unique insight into the potential diagnostic ability of Raman spectroscopy for colorectal cancer.

To optimise the nanoparticle functionalisation and SERS detection an initial programme of work will study the blood, tissue and faecal samples from patients with advanced disease and establish the optimal antibody pairing from a potential panel of five antibodies associated with colorectal cancer cells.

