7.1 Sample Size

1,800 patients will be included in the study to provide a representative number in each subgroup for the purposes of this study.

Based on analysis from our pilot data (currently at n=200) the 300 samples per subgroup are predicted to provide the required independent validation test set to achieve over 85% sensitivity and specificity with 80% power at the 95% confidence interval.

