7.2 Statistical Analysis

Statistical analysis and feasibility: The spectral analysis will be conducted using in-house principle component analysis (PCA) tools. This type of analysis is excellent for discriminating subtle spectral differences and determining commonality within datasets. The key aspect here will also include using the principle component loadings to ascertain the origin of the spectral differences, i.e. linking the spectral changes to macromolecular changes in the samples. Specially, by combining principal component analysis and hierarchical cluster analysis, the statistical difference between Raman spectra of different patient groups can be revealed effectively leading to specific accuracy, sensitivity and specificity measures. The research will also consider the development of PCA-based algorithms to establish calibration PCA loadings which can be run against ‘unknown’ samples. These new tools will enable the development of a

diagnosis platform and hence establish the route towards early diagnostics and personalised medicine.

8. Data Handling & Record Keeping

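### Section 7.1 counts all 300 samples per subgroup as an independent validation set, but sections 4.3 and 7.2 tune and assess the test on those same groups with no lock point, so independence is claimed and not secured

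*Protocol*

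**What the plan says.** - **Sample size (Protocol 7.1).** The only justification for the group size is that "the 300 samples per subgroup are predicted to provide the required independent validation test set", in order "to achieve over 85% sensitivity and specificity with 80% power at the 95% confidence interval". The prediction rests on pilot data, 200 at the time of writing. The section does not say whether those 200 are part of the 1,800.
- **Wavelength (4.3).** The instrument offers 785 nm and 532 nm, and "Comparisons across different patient groups will help determine the best wavelength conditions for reliable data acquisition, sample handling and data reproducibility".
- **Antibodies (4.3).** A preliminary piece of work on patients with advanced disease is to "establish the optimal antibody pairing from a potential panel of five antibodies associated with colorectal cancer cells".
- **Accuracy (7.2).** Principal component analysis combined with hierarchical clustering of the patient groups is expected to yield the accuracy, sensitivity and specificity figures. The investigators will also consider the "development of PCA-based algorithms to establish calibration PCA loadings which can be run against" unknown samples. The section does not say which patients supply the loadings or the unknowns.
- **Group 8 (3.1).** In 300 symptomatic primary-care patients, a positive, equivocal or negative test result is compared with the final diagnosis. These data are to inform a later interventional study.

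**The concern.** A validation set is independent only if nothing about the test was decided on it. Section 7.1 gives the 300 per subgroup that role. Sections 4.3 and 7.2 give the same groups development roles: comparing them helps to settle the wavelength, and clustering them produces the accuracy figures. The protocol names no development patients and no moment when wavelength, antibody pair, number of components, loadings and cut-offs are frozen.

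Followed as written, the accuracy would be an in-sample figure presented as a validated one. With a target of over 85%, a few points of optimism can decide whether the test appears to succeed. The loss is also hard to repair, because spectra that have been compared across groups to make choices cannot later serve as untouched validation data. Group 8 could be a clean evaluation cohort, but nothing fixes the three-way result rule before it is applied there.

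**Working it through.** **1. Are any patients left over for development?** Group sizes from the synopsis: 300 + 300 + 200 + 300 + 80 + 20 + 300 + 300 = 1,800, which is the total in 7.1. Every patient belongs to a group with a stated purpose, and none is set aside. The pilot 200 may or may not be additional.

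**2. Can the figure of 300 be reproduced?** Not from the stated inputs, because 7.1 gives neither a null value nor a precision target. For a one-sample proportion,

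n = [(1.96·√(p0·(1−p0)) + 0.842·√(p1·(1−p1))) / (p1−p0)]²

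with two-sided 5% and 80% power. For p0 = 0.85, p1 = 0.90 gives 363 and p1 = 0.905 gives 297. So 300 fits a true value near 90.5%, but that value is not in the protocol. It is used below only as an assumption.

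**3. How much could choosing a setting on the validation data add?** Assume that every setting truly has 85% sensitivity and that the best observed one is kept. The optimism is E[max of m binomial proportions] − 0.85, computed exactly under independence.

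- Two wavelengths, m = 2, n = 300: 1.2 points.
- Two wavelengths × C(5,2) = 10 antibody pairs, m = 20, n = 300: 3.7 points.
- Settings measured on the same patients would be correlated. By normal approximation, with SE = √(0.85·0.15/300) = 2.06 points and an expected maximum of 20 standard normals of 1.87, the optimism is 1.87·√(1−ρ)·2.06. That is 2.7 points at ρ = 0.5 and 1.7 at ρ = 0.8 (both correlations assumed).

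**4. How much could in-sample fitting add?** This was simulated with linear discriminant analysis on component scores, 300 patients per arm and a true signal of about 85%. The numbers of components and settings are assumptions. The gap between apparent accuracy and accuracy in new patients was under 1 point with few components and no selection. With one setting it was 1.6 points at 20 components (85.8% against 84.2%) and 4.0 points at 50 components (87.0% against 83.0%). With the best of 20 settings kept, the gap was about 3 to 6 points.

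**5. What if patients are held back from the 300?** The intervals are Wilson 95% intervals at an observed 85%. Power is exact binomial, for showing more than 85% at one-sided 0.025 when the true value is 90.6% (assumed).

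| Held out | 95% interval | Successes needed | Power |
|---|---|---|---|
| 300 | 80.5% to 88.6% | 268 | 80% |
| 200 | 79.4% to 89.3% | 181 | 58% |
| 150 | 78.4% to 89.8% | 137 | 45% |
| 100 | 76.7% to 90.7% | 93 | 27% |

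**The case against.** The strongest reply is that the protocol never says the same patients choose, train and test, and that a split or cross-validation scheme is commonly left to a statistical analysis plan, which is not at hand. Several stronger readings are tempting and go beyond the text:

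- **That the validation set is definitely not independent.** The pilot 200 may lie outside the 1,800 and could be the training set. Section 7.2 at least distinguishes calibration loadings from unknown samples.
- **That wavelength is chosen to maximise accuracy.** Section 4.3 gives reliability, handling and reproducibility as the aims. Choosing on those inflates accuracy less, or not at all.
- **That the antibody pair is tuned on group 1.** It is a preliminary programme in advanced disease and is not tied to the 300 of group 1. The figure of 3.7 points is therefore an upper-end case.
- **That groups 1, 5 and 6 share patients.** Recruitment from the same multidisciplinary meeting makes this possible, but the documents do not state it, and the group sizes sum to 1,800 patients.
- **That inflated figures from all groups will plan the interventional study.** Section 3.1 ties that planning to group 8 only.

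All of these limits stand. The appeal to an analysis plan does not dispose of the point, because the protocol itself rests its sample size on independence and itself describes tuning and assessing on the same groups. If an analysis plan took development patients out of the 300, the validation set would be smaller than 300 and 7.1 would have to change. The study's exploratory character lowers the stakes but does not make the label accurate.

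**Conclusion.** The point holds as a conflict between 7.1 and sections 4.3 and 7.2: independence is asserted, and nothing in the protocol delivers it. The accuracy may be optimistic; the text does not establish that it will be. From selection alone, at n=300 and a true 85%, the size is about 1 point (two wavelengths, chosen on sensitivity) to about 4 points (20 independent settings, all tried on the validation patients). Any optimism from fitting components and cut-offs in-sample comes on top and depends on their number. It could be negligible if the wavelength is chosen purely on reproducibility and the test is built entirely on pilot samples outside the 1,800, but the protocol would have to say so.

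**What to change.** Amend 4.3, 7.1 and 7.2 together.

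- **Development set.** Name it, fixed by patient: the pilot samples, stating whether they lie inside the 1,800, plus if needed a pre-listed part of the cancer and control groups. Controls must be included so that choices are made on discrimination.
- **Lock.** Choose wavelength, antibody pair, number of components, loadings and the cut-offs for positive, equivocal and negative on that set only, and freeze them before validation.
- **Validation.** Apply the frozen test once, blind to diagnosis, to the remaining patients and to group 8. Keep all samples of one person on the same side, which matters most for groups 5 and 6 with their serial samples.
- **Sample size.** Restate 7.1 for the number actually held out, with an explicit null value or precision target.

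The administrative cost is wording and a locked list of study numbers. The statistical cost depends on the split. If the pilot alone is the development set, the 300 can stand and nothing is lost. If 100 of 300 are moved to development, the interval widens from about ±4 to ±5 points, and power to show more than 85% falls from 80% to about 58% under the assumptions above. That loss should be either accepted openly or met by enlarging the groups concerned.

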5.5 Sample storage procedures

All samples will either be analysed within 3 days of collection to minimize the chance of degradation, or stored at -80 degrees C until analysis. After analysis, all samples will be destroyed in accordance with the Human Tissue Act.

6. Safety measures

The safety of trial subjects will precedence over any other aspect of the trial. Consequently, prior to the initiation of laboratory work, lines of communication will be established with the study sponsor, to ensure that any issues that may impact on patient safety are reported without delay. These may include, but are not limited to, the reporting of unexpected or out of range results and significant deviations from the clinical protocol or work instructions.

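### Assay development uses advanced-cancer samples only, and nothing keeps those spectra out of the comparison with controls, so part of a group 1 versus group 4 difference can be an assay-version difference

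*Protocol*

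**What the plan says.** **Sequence (Protocol 4.3).** The stated purpose of the opening phase is "To optimise the nanoparticle functionalisation and SERS detection". For this, "an initial programme of work will study the blood, tissue and faecal samples from patients with advanced disease", and the team will "establish the optimal antibody pairing from a potential panel of five antibodies associated with colorectal cancer cells". Advanced disease is the only patient category named for this phase.

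**Other assay settings (Protocol 4.3).** Wavelength and handling are also still open, but these are studied more widely: "Comparisons across different patient groups will help determine the best wavelength conditions for reliable data acquisition, sample handling and data reproducibility".

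**Source of the samples (Protocol 3.1, 4.4).** Group 1 is 300 patients with T3/4 cancer, sampled before surgery. It is the only group that gives faeces; groups 2 to 8 give blood only.

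**Storage and destruction (Protocol 5.5).** Samples are either "analysed within 3 days of collection to minimize the chance of degradation, or stored at -80 degrees C until analysis". Then: "After analysis, all samples will be destroyed in accordance with the Human Tissue Act".

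**Volume (Protocol 5.1).** Each Raman analysis needs 5 mL of blood, and groups 1 to 4 each give one 5 mL sample.

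**Validation count and analysis (Protocol 7.1, 7.2).** Section 7.1 treats the 300 samples per subgroup as the independent set for validation. Section 7.2 says that by PCA with cluster analysis "the statistical difference between Raman spectra of different patient groups can be revealed effectively", which is to lead to accuracy, sensitivity and specificity.

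**The concern.** The primary objective (Protocol 2.1) is an association between spectral signature and colorectal malignancy. PCA describes whatever variation is in the spectra. It cannot tell a shift caused by disease from one caused by a different antibody pairing or nanoparticle preparation. If some cancers are read while the assay is being developed and every control is read afterwards, assay version becomes a partial marker of cancer status.

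Three stated rules combine to allow this. The development phase draws on cancer samples only. Samples are destroyed after analysis, so the early ones may not be available for the final assay. All 300 group 1 samples are counted for validation, with no allowance for those spent on development. A false signature, and somewhat inflated sensitivity and specificity, could follow. Where version and group coincide, no later analysis can separate them.

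**Working it through.** **The plan's own figure.** Section 7.1 gives 300 per subgroup for over 85% sensitivity and specificity with 80% power at 95% confidence. It states no null value or interval width, so 300 cannot be reproduced uniquely. At a true 85% with n = 300, the 95% half-width is 1.96 × √(0.85 × 0.15 / 300) = 4.0 points. Exact power is 81% against a null of 78.5% (two-sided 5%). The figure is attainable under some nulls. What matters here is that it counts the whole of group 1.

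**Inputs for the bias.** From the protocol: 300 in group 1 and 300 in group 4. Assumed, because the protocol gives neither:
- f, the share of group 1 measured on a development version, with no controls measured on it;
- d, the shift between versions on one spectral score, in SD units.

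There is taken to be no true disease effect.

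**Formula.** An early cancer compared with a control is ranked higher with probability Φ(d/√2), and a later cancer with probability 0.5. So

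AUC = f × Φ(d/√2) + (1 − f) × 0.5.

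Φ(0.5/√2) = 0.638 and Φ(1.0/√2) = 0.760.

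| Share of group 1 measured early | AUC, d = 0.5 | AUC, d = 1.0 |
|---|---|---|
| about 50 of 300 (f = 1/6) | 0.5 + 0.138/6 = 0.523 | 0.5 + 0.260/6 = 0.543 |
| one third | 0.5 + 0.138/3 = 0.546 | 0.5 + 0.260/3 = 0.587 |
| all (upper bound) | 0.638 | 0.760 |

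**False-positive rate.** A two-sided 5% z-test of the mean score, 300 versus 300, was simulated 400 times per setting:

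| Share early | d = 0.5 | d = 1.0 |
|---|---|---|
| 51 of 300 | 18% | 54% |
| 99 of 300 | 53% | 98% |
| all | 100% | 100% |

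Check for 50 early and d = 0.5: the mean difference is f × d = 0.083, its standard error is √[(2 + f(1 − f)d²)/300] = 0.082, and the expected z is 1.01. The rejection rate is then about 17%, in line with the simulation.

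**With balance.** If the same share of cancers and controls is measured on each version, the false AUC is 0.50 whatever d is. Simulated false-positive rates were 0.5% to 6% for d from 0.25 to 2.

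**Cost of exclusion.** Leaving out 50 or 100 group 1 samples widens the half-width for sensitivity from 4.0 points to 1.96 × √(0.1275/250) = 4.4 or 1.96 × √(0.1275/200) = 4.9 points.

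**The case against.** The strongest reply is that the protocol does not say these development spectra enter the comparison. It does not name group 1 as their source, and tissue is included although sections 3.1 and 4.4 do not list it for group 1. Section 7.1 speaks of an independent validation set and of pilot data already at n = 200, and 7.2 plans to run calibration loadings against unknown samples. All this suggests that development and test data were meant to be separate. Storage at -80 °C would allow cancers and controls to be run together. Run order and exclusions could also sit in a laboratory procedure or an SAP not shown here.

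Part of this stands. The link to group 1 is an inference, though a reasonable one, since no other group gives faeces. The intention to separate the data may well exist. But 7.1 counts all 300 per subgroup as validation data, which leaves no room for samples spent on development. Frozen storage is optional and tied to no run order. An SAP could drop the development spectra, but it could not restore destroyed samples or separate version from group where they coincide.

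A reader might infer more than the text supports:
- **That all cancers are measured before all controls.** The protocol does not say so. Group 2, with 300 T1/2 cancers, lies outside an advanced-disease programme. Even if all of group 1 were early, that is half of the 600 cancers in groups 1 and 2, and the AUCs for the pooled comparison fall to 0.57 and 0.63.
- **That wavelength is part of the cancer-only phase**, giving ten antibody pairs times two wavelengths. Section 4.3 places wavelength and handling in comparisons across groups.
- **That destruction causes the bias.** It only removes the chance to re-measure, and 5.5 does not say whether analysis means the first reading or the completed work.

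**Conclusion.** The point holds as a design weakness of unknown and possibly small size. The cancer-only development phase, the destruction rule and the full count of 300 are stated in the protocol. Together they let cancer status overlap with assay version in the group 1 versus group 4 comparison.

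The size rests on two assumed quantities. If the initial programme takes about 50 samples, the false AUC is close to 0.5, though a significance test would still reject too often. The values for all of group 1 measured early are an upper bound and not a forecast. Even then, a version shift would have to reach 2 × Φ⁻¹(0.85) = 2.07 SD to produce 85% sensitivity and 85% specificity by itself. The calculation therefore does not show that any accuracy the study reports would be an artefact. It shows that the plan as written could not rule out a contribution from the assay. The sponsor should correct this because the change is cheap and the problem may not be repairable afterwards.

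**What to change.** **Section 4.3.** Fix the antibody pairing and SERS conditions before the group comparison begins. Measure all groups to be compared on that one version, in runs that mix groups in random order, using the -80 °C storage already allowed.

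**Section 5.5.** Destroy samples only after that run is complete.

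**Sections 7.1 and 7.2.** Leave initial-programme samples out of the group comparison and the validation count, and restate the group 1 validation number. Re-run such a sample on the fixed assay only if enough serum remains; 5.1 asks for 5 mL per analysis and group 1 gives one 5 mL sample, so this may often be impossible.

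**Cost.** A somewhat smaller group 1 validation set, freezer space, later destruction and a run list. No extra patients or visits are needed.

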4.4 End of Study Definition

Groups 1-4 will be in the study for 1 month to allow a single biological sample to be taken (of blood and/or faeces in group 1, and blood only in groups 2-8), and to allow a precise diagnosis and cancer stage where appropriate to be recorded.

Group 5 will be enrolled for 6 months to permit serial blood sampling (n=4) at diagnosis, during and after completion of chemoradiotherapy, and after subsequent surgery.

Group 6 will be enrolled for 2 years to allow 5 blood samples to be obtained during this standard follow up period. In the event of the death of the participant during the follow up period then only samples collected up to that timepoint will be measured.

4.5 Subject Withdrawal

Subjects will be withdrawn from the study under the following circumstances:

- Withdrawal of consent

4.6 Data Collection and Follow up for Withdrawn Subjects

Patients who withdraw consent may not wish their data to be used. If this is the case then it will be deleted.

5. Laboratories

5.1 Laboratory assessments

Raman analysis- 5mL blood will be required for each Raman analysis. Groups 1,2,3 and 4 will only require one blood sample (5mL total volume). Group 5 will have blood sampling on 4 occasions of 5mL per sample *ie* 20mL total. Group 6 will have 5mL of blood taken on 5 separate occasions *ie* 25mL blood in total.

Blood samples will be transferred to the Centre for NanoHealth laboratory in ILS-2 on ice to maintain the sample at 4 degrees centigrade. Faecal samples will be transported at room temperature.

5.2 Local laboratories

All analysis will take place at the Centre for NanoHealth laboratory in ILS2 at Swansea University.

5.3 Sample labeling/logging

Samples will be pseudo-anonymised with a unique study number and date of collection.

5.4 Sample receipt/Chain of Custody/ Accountability

All samples received by the laboratory will be assessed on arrival to check their physical integrity. If samples have been compromised in transit the researcher will be notified promptly. On receipt, laboratory staff will ensure that all samples are accounted for and this process will be documented. If samples are poorly labeled, missing or if unexpected samples are received, the study sponsor will be notified. Samples with labeling that does not meet the laboratory's minimum acceptance criteria will be rejected and disposed of according to policy.

Each sample received at the laboratory will be appropriately and uniquely identified.

Mechanisms will be in place to track the movement of each sample from arrival

to storage and to analysis. Transportation of samples will be undertaken according to the ABMU Health Board/ Public Health Wales Pathology Department transportation policy Adequate provision will be made to ensure that the laboratory in the Centre for NanoHealth and ILS-2 has sufficient capacity for the storage of refrigerated and frozen samples in the event of malfunction. All refrigerators and freezers will have temperature control logs maintained for QA as routine.

